# **Effectiveness of the CDK-SMS nursing intervention for adults with chronic kidney disease**

**July 20, 2022**

## **Scope and justification of the proposal**

Chronic kidney disease is a complex pathology, where the person who suffers from it is faced with unexpected changes in their customs and lifestyles, in addition to complying with a strict therapeutic regimen, because from its diagnosis it seeks to delay progress of this, and the prevention of complications derived from its development (1). Within the disease management guidelines at the European level, which were necessary for the Colombian context, they recommend that the factors associated with disease progression should be addressed, which include: "the cause of the disease, the level of the glomerular filtration rate, the level of albuminuria, age, sex, race / ethnicity, elevated blood pressure, hyperglycemia, dyslipidemia, smoking, obesity, history of cardiovascular disease, continued exposure to nephrotoxic agents and others" (2–4), most of which are modifiable, through self-management interventions.

Self-management interventions aimed at adults with CKD in early stages contribute to improving the quality of life, self-management behaviors and self-efficacy, but above all in the prevention of complications derived from the disease. Preventing a person with CKD from progressing to advanced stages or terminal management phases leads to lower health care costs by delaying the start of specialized treatments (renal replacement therapies) that require high technology and preventing complications that can lead to an increased mortality in the population. Results that have been considered within health policies and therefore have become a premise that justifies the relevance of the nursing intervention in self-management (5–9).

The nursing intervention in self-management implies advancing in approaches where adults with early-stage CKD are active agents in managing their own care towards awareness and responsibility for the daily care of the disease (5,10). Today there is a nursing intervention in self-management the CKD SMS, designed specifically for the population object of this study, which has been administered in two countries where there are different socio-economic and cultural characteristics (Vietnam and Australia), demonstrating feasibility in its implementation and acceptability by the participants, in addition to being effective in promoting self-management behaviors, a comprehensive and novel construct (8,11–14), which is achieved through the manipulation of self-efficacy.

In the present proposal, therapeutic adherence is a central concept since it is expected that when performing the nursing intervention in self-management, adherence to the therapeutic regimen will increase, evidenced in the exercise of healthy habits, such as the intake of a diet in accordance with its condition and the reduction of risk factors inherent to the disease, also translated into the impact of these factors on clinical control variables such as: improving blood pressure control, glycosylated hemoglobin levels, but also an important impact in delaying the progression of the disease, which is evidenced not only by not requiring renal replacement therapies, but also by maintaining or improving the

glomerular filtration rate, which is beneficial for both the person and for the health system (15–17).

The nursing professional plays an important role in the execution of self-management interventions such as the CKD SMS, since it is who within the health team has the responsibility of imparting education and monitoring people, in the investigations found in most of the Regarding the interventions that have been carried out, the participation of the nursing professional has been fundamental since it is the one who is in constant interaction with the person.

### **Research contributions to public policies**

Chronic kidney disease (CKD) represents a catastrophic public health problem that is growing worldwide, affecting 10% of the world's adult population (18). In Colombia, the high-cost account reported a prevalence of 3.5 cases per 1,000 inhabitants (19), ages ranging from 50 to 80 years. 90% of cases are in primary stages (stages 1,2,3 and 4), which do not require renal replacement therapies and in these stages, there is a window of opportunity to promote changes in lifestyles, adherence Therapeutic and self-management as intervention measures that can contribute to the prevention of disease progression, complications derived from it, and these variables have so far not been considered comprehensively in previous studies.

In response to this problem, the World Health Organization calls attention to a comprehensive approach to chronic kidney disease, which should be aimed at improving the understanding, measurement, prevention and even treatment of it, also affirming that said approaches will contribute to the social appropriation of knowledge and the reduction of the burden of this disease in the future. The National Kidney Foundation (NKF), in its work to support the formulation of public policies, has reported the importance of health education and primary care, for the benefit of people's well-being and quality of life (20).

At the national level, in addition to the clinical practice guide where care is framed and self-management is mentioned as an approach tool, there are important regulations from the current health model, this has special strategies within which it must be addressed the care of people with CKD and makes explicit the importance of management from the early stages. Said strategies (19) are: primary health care that seeks to provide comprehensive care where disease prevention, diagnosis, treatment, and rehabilitation are found.

Within primary care, there is a relevant strategy in the management of CKD, called health risk management, which is transversal within the comprehensive health care policy, this strategy is based on the articulation and interaction of the system agents in order to "identify, measure, intervene from prevention to palliation and carry out follow-up, monitoring and evaluation of risks to the health of people, families and communities, aimed at achieving results in health and well-being of the population "(2).

Derived from this strategy, resolution 2565 of 2007 (21) was created, in which chronic kidney disease is defined as a high-cost disease, translated into mandatory notification of both the disease and also those precursor pathologies such as hypertension and diabetes ; Following the path of risk management, the high cost account in 2016 in its circular 0038 (22), determines the adoption of the 4X4 strategy proposed by the WHO, which emphasizes the work for the implementation of interventions that are effective based on evidence to reduce risk factors and reduce the prevalence and mortality of non-communicable diseases, which for this case specifically is CKD.

A tool that implements all the guidelines in the approach to the disease is the acquisition of self-management behaviors in people with CKD in early stages, which allows them to have a participation in the control of their health, making correct and informed decisions, but above all with the conviction in himself of being able to maintain his state of health, control and achieve objectives in relation to his disease, through the stimulation of self-efficacy.

### **Research question**

How effective is the CKD SMS self-management nursing intervention on self-management behaviors, self-efficacy, and adherence in adults with early-stage CKD compared to usual care?

### **General objective**

To determine the effectiveness of the self-management nursing intervention (CKD SMS) on self-management behaviors, self-efficacy, and therapeutic adherence in people with CKD in early stages compared to usual care.

### **Specific objectives**

1. Describe the sociodemographic and clinical characteristics of the control group and the experimental group.
2. Establish the level of self-efficacy, self-management behaviors and therapeutic adherence as a baseline in people with chronic kidney disease in early stages.
3. To evaluate the changes in self-management behaviors, self-efficacy, and therapeutic adherence post-intervention and in the control group at 16 weeks.

### **Hypothesis:**

- Establish that the CKD SMS intervention has a positive effect on self-efficacy and therapeutic adherence in people with early-stage CKD compared to usual care.
- Establish the effectiveness of the CKD SMS intervention in improving self-management behaviors compared to the usual intervention in people with CKD in early stages.

## **METHODOLOGY**

This is a quantitative investigation, with a pragmatic randomized clinical trial (pRCT) design, parallel experimental type, given the one-to-one allocation in two parallel groups with repeated pre-test and post-test measures, considering that this type of study is useful for evaluating interventions in usual care (23). In CKD, the use of a pRCT enables a broader range of patients to be included to test an intervention applicable to patient care and to measure relevant patient-centered outcomes, thus improving external validity and translation of the results into the clinical care (24).

Where the outcome variables are: Self-management behaviors (primary), self-efficacy and therapeutic adherence (secondary). The population will be adult men and women with chronic kidney disease in stages 1-4, who attend control of their disease or belong to the BBraun Avitum Prevenser program.

#### **Relevance of effectiveness measurement:**

Assuming that effectiveness refers to "the effects of an activity and its final results, benefits and consequences for a population in relation to the established objectives" (25), it is pertinent to measure this within the present study, since it is sought to really determine that the CKD SMS intervention improves the self-management behaviors of people with CKD in their real context, hence this measurement is the objective even of pragmatic clinical trials. And it differs from the efficacy that is more related to randomized clinical trials since they look for the "degree to which the intervention produces the hypothetical effects under ideal conditions" (26).

## **POPULATION**

**Target population:** Adult men and women with chronic kidney disease in stages 1-4, with different characteristics such as educational level, socioeconomic status, and marital status. Taking into account that the definition of early stages through the criteria demarcated by the Colombian clinical practice guideline, where the glomerular filtration rate (GFR) is the indicator for stratification as follows: stage 1 people with a GFR less than or equal to 90 (ml (min / 1.73 m^2), stage 2 people with GFR between 60-89 (ml (min / 1.73 m^2), stage 3 people with GFR between 30-59 (ml (min / 1.73 m^2)) and stage 4 people with GFR between 15-30 (ml (min / 1.73 m^2) who attend kidney protection programs of the Renal Units in Colombia.

**Accessible population:** Adult population men and women with chronic kidney disease in stages 1-4, with different characteristics such as educational level, socioeconomic status, marital status, those who attend control of their disease or belong to the Prevenser program of the BBraun Avitum, in Colombia, which can be found in the databases provided by Prevenser program.

**Sampling frame:** Database provided by Prevenser program population: It will be those participants who meet the inclusion and exclusion criteria, which are:

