#### **Inclusion criteria**

- Adults, of legal age for Colombia (18 years), with a diagnosis of chronic kidney disease in stages 1-4, without renal replacement therapy according to the Kdigo guidelines.
- People without comorbidity and with non-decompensated or exacerbated chronic comorbidities.
- People in use of their mental and communication faculties.

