#### **Exclusion criteria**

- People who are under the effect of some substance that alters the mental state.
- People under 18 years of age.
- Being receiving renal replacement therapy or being in a terminal stage.
- Illiterate people.
- People who are participating in another educational intervention different from the usual care.

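### Do the contradictory GFR bands for CKD stages 1 to 4 leave the study population undefined?

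*Combined protocol and SAP*

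**What the plan says.** In the combined protocol and SAP, the target-population paragraph under POPULATION attributes its definition of early stages to the Colombian guideline and says that "the glomerular filtration rate (GFR) is the indicator for stratification as follows". It then lists four bands:

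- "stage 1 people with a GFR less than or equal to 90"
- "stage 2 people with GFR between 60-89"
- "stage 3 people with GFR between 30-59"
- "stage 4 people with GFR between 15-30"

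These are the only numeric stage limits in the document. The same section describes the sampling frame, drawn from the Prevenser database: "It will be those participants who meet the inclusion and exclusion criteria". The inclusion criterion asks for adults "with a diagnosis of chronic kidney disease in stages 1-4, without renal replacement therapy according to the Kdigo guidelines" and gives no GFR limits. The relevant exclusion reads "Being receiving renal replacement therapy or being in a terminal stage", again without a GFR value.

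**The concern.** Stage 1-4 disease defines who the trial is about: the research question, the objectives and the hypotheses all refer to early-stage CKD. If the definition of the stages contradicts itself, a reader could fairly ask whether the population is defined at all, whether staff at screening could admit or turn away the wrong people, and whether a table of stage by group could be trusted.

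The stage 1 limit is spelled out in words, so it is not a symbol lost when the PDF was read, and nothing in the sentence is blacked out. There are two separate defects: the direction of the stage 1 limit, and the value 30 shared by stages 3 and 4. The word stratification in the same sentence may add to the worry by suggesting that the bands feed a stratified randomisation.

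**Working it through.** **Inputs.** The four bands quoted above: stage 1 at or below 90, stage 2 from 60 to 89, stage 3 from 30 to 59, stage 4 from 15 to 30. The plan states no figure to reproduce, so the check is to place each whole-number GFR in every band that contains it.

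**Bands as written.**

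| GFR | Stages | Whole-number values |
|---|---|---|
| 0-14 | 1 | 15 |
| 15-29 | 1 and 4 | 15 |
| 30 | 1, 3 and 4 | 1 |
| 31-59 | 1 and 3 | 29 |
| 60-89 | 1 and 2 | 30 |
| 90 | 1 | 1 |
| above 90 | none | - |

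From 15 to 90 there are 15 + 1 + 29 + 30 + 1 = 76 values, of which 15 + 1 + 29 + 30 = 75 fall in more than one stage. This count looks alarming, but it is one misworded phrase counted 75 times.

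**Stage 1 limit reversed (90 and above), all else unchanged.** 15-29 is stage 4, 31-59 is stage 3, 60-89 is stage 2, and 90 upward is stage 1. Only 30 still has two stages. Because the other three bands descend in order from 89, this reading is the one the text itself points to.

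**Effect on eligibility.** All four stages are eligible, so what matters is whether a value lies in any band, not in which one.

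- As written, the bands together cover every GFR up to 90.
- With stage 1 reversed, they cover whole numbers from 15 upward.
- From 15 to 90, every whole number is covered either way, so overlaps in that range, including the one at 30, cannot change who may enter.
- The two readings differ only above 90 and below 15.

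Above 90, the inclusion criterion admits a person diagnosed with stage 1 disease whatever the paragraph's number says. Below 15, the criterion requires a diagnosis of stages 1-4 and the terminal-stage exclusion applies. That a value below 15 is terminal is an inference from the lower end of the stage 4 band, since the exclusion gives no number.

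**Where stage is used.**

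- Sample size (SAMPLE): a mean difference of 18.13 with 80% power and 95% confidence. Stage plays no part.
- Randomisation (SAMPLE): a random-number table and sealed envelopes, with no stratification factor. The stratification in the population paragraph is clinical staging.
- Confounders (STUDY VARIABLES): age, gender, education, time of diagnosis and other comorbidities. Stage is not named.
- Analysis (APPROACH TO THE ANALYSIS FRAMEWORK): stage is not mentioned. The comparison of clinical characteristics between groups could include it.

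**The case for a change.** The best argument for a change is that the text is wrong, the correction is one line, and no other section supplies the right limits. The population paragraph names the Colombian guideline while the inclusion criterion names KDIGO, and only the former comes with numbers. Someone repeating the trial could not stage patients from this text. Correcting the stage 1 limit alone would still leave 30 in two stages. Disease-related characteristics are listed among the independent variables, so stage may well be collected and tabulated, and might be considered for the adjusted model.

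All of this is true of the wording, and the defect should be acknowledged. It does not show that the trial would do anything differently. No section tells staff to assign stage from these numbers; the sampling frame is tied to the inclusion and exclusion criteria. If stage is tabulated, the analyst can take the recorded diagnosis. If it is instead computed from GFR, one convention for the value 30 applied alike to both randomised groups favours neither. The same holds for any value recorded to a decimal place that falls between 59 and 60 or between 89 and 90.

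**Conclusion.** The inconsistency is real but clerical: one reversed limit and one shared boundary value in a descriptive paragraph. No effect on enrolment, randomisation, sample size or the treatment comparison is shown. What remains uncertain is how a GFR of 30 would be labelled in a baseline table, if stage is tabulated from GFR at all.

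This rests on two assumptions: that patients are entered on an existing stage 1-4 diagnosis, as the inclusion criterion says, and that nobody screens from the literal numbers in the population paragraph. If somebody did, only people above 90 or below 15 could be handled differently, and how many that might be cannot be worked out from the documents. Tidying the sentence at a convenient revision would do no harm, but nothing in the design or the analysis depends on it.

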#### **Inclusion criteria**

- Adults, of legal age for Colombia (18 years), with a diagnosis of chronic kidney disease in stages 1-4, without renal replacement therapy according to the Kdigo guidelines.
- People without comorbidity and with non-decompensated or exacerbated chronic comorbidities.
- People in use of their mental and communication faculties.

#### **Exclusion criteria**

- People who are under the effect of some substance that alters the mental state.
- People under 18 years of age.
- Being receiving renal replacement therapy or being in a terminal stage.
- Illiterate people.
- People who are participating in another educational intervention different from the usual care.

### **SAMPLE**

**Sample design:** The sample size was calculated through probability sampling, since individuals have the same probability of being chosen. On the other hand, of the comparison of means in independent groups, assuming a power of 80%, a confidence level of 95%, an expected mean difference of 18.13 in the improvement of self-management, reported by previous studies (6,27).

**Sample size:** A total of 82 participants (41 per group), in addition, a mortality of 20% of the participants is expected, so a total sample of 100 participants (50 per group) will be assumed. made in the Epidat 3.1 program.

**Randomization:** Participants will be randomized into two groups, using sequentially numbered opaque sealed envelopes, where the investigator and participants will be blinded to the allocation of each group. For the generation of the randomization sequence, it will be developed by the investigator by means of the realization of a table of random numbers in the Epidat 3.1 program to eliminate the selection bias, in the same way, said table will be verified to guarantee balance between the number of participants assigned to each group (control and intervention).

**Blinding:** In view of the need to minimize bias, both the participants and the recruitment research assistant will be blinded until allocation. The Result Research Assistant will not have access to the allocation base, nor to the allocation codes. On the other hand, it is

declared that the intervention will be given by the researcher and that the main researcher will also participate in statistical analysis, therefore, the study is classified as single blind.

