## **BIAS CONTROL**

### **Internal validity**

**- Selection and performance bias:** to avoid this bias, random selection will be carried out by delimiting the population and defining the sampling frame in detail, being adequate for the study design; in addition to the generation of a list of the patients who attend the controls, for the assignment of random numbers and the appropriate method for this by means of a software. On the other hand, allocation concealment will be carried out with sealed envelopes containing the allocation number; Within the calculation of the sample, an additional 20% is initially added as prevention of losses in the groups, additionally the intervention protocol will be carried out faithfully and the largest portion of the contact data of the participants will be taken in order not to lose the contact and their participation in the follow-up.

**- Performance and arrest bias:** A single-blind study will be carried out in which the allocation to the participants will be blinded, since the intervention and the analysis of the results will probably have to be developed by the main investigator and therefore this cannot be blinded. But to have faithful results, the data collection (application of the instruments) will be supported by a research assistant who will also be blinded to the assignment of the participants to the control group or experimental group.

**- Attrition bias:** The collection of the information will be meticulous in order not to lose any data, and, in addition, a percentage addition will be made in the calculation of the sample to predict the mortality of the participants.

**- Reporting bias:** The delivery of the results without missing the expected results in accordance with the methodological approach, in the same way, will be its publication.

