### **APPROACH TO THE ANALYSIS FRAMEWORK**

To respond to specific objectives 1 and 2, a statistical analysis will be carried out through descriptive statistics. Subsequently, a normality test will be carried out, to identify how the data distribution is presented, in addition, it is carried out to determine the tests to be used, whether parametric or non-parametric in the inferential analysis, bivariate and multivariate analysis. A bivariate analysis, to compare the sociodemographic and clinical characteristics between the groups.

To respond to specific objective 3, Inferential statistics will be carried out, which will be carried out to accept or reject the null or alternative hypothesis, which are proposed as:

- H1: The CKD SMS intervention in self-management in people with CKD in early stages is effective on self-management behaviors, self-efficacy, and therapeutic adherence. (H1: G1 > G2; p < 0.05)
- H0: The CKD SMS intervention in people with CKD in early stages is not effective on self-management behaviors, self-efficacy, and therapeutic adherence. (H0: G1 = G2; p > 0.05)

But it is also used multivariate analysis, to determine the individual relationship but also the relationship of the possible variables that intervene on the results, a simple logistic regression model will be built and adjusted according to the possible confounding variables.

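### The 20% loss allowance falls slightly short: 100 participants less 20% leaves 80 (40 per group), not the required 82 (41 per group)

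*Combined protocol and SAP*

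**What the plan says.** Under SAMPLE (Sample design), the calculation is a comparison of means in two independent groups, "assuming a power of 80%, a confidence level of 95%, an expected mean difference of 18.13". No standard deviation is given, and this text does not say whether the test is one- or two-sided.

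Under SAMPLE (Sample size), the result is "A total of 82 participants (41 per group"). The same sentence goes on: "a mortality of 20% of the participants is expected, so a total sample of 100 participants (50 per group) will be assumed".

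BIAS CONTROL (Internal validity) refers to the allowance twice. The item on selection and performance bias says: "Within the calculation of the sample, an additional 20% is initially added as prevention of losses in the groups". The item on attrition bias says that "a percentage addition will be made in the calculation of the sample to predict the mortality of the participants". Taken together, these show that mortality here means loss of participants, not only death. Neither item says what the 20% is a percentage of. The document gives no other loss rate and no rule for replacing participants who are lost.

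**The concern.** The Sample size sentence links three figures: a requirement of 82, an expected loss of 20%, and an enrolment target of 100 that is presented as following from the other two. It does not follow. An allowance for loss has to leave the required number after the loss has occurred, so the requirement must be divided by the proportion retained. Adding the loss percentage to the requirement always gives too few.

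What is at stake is mainly the consistency of the plan. It names this allowance as its safeguard against attrition. If loss turns out exactly as predicted, the final report will show fewer participants than the protocol says are needed for 80% power, and nothing in the protocol explains the gap.

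**Working it through.** **Inputs.** All are from the SAMPLE section: required number 41 per group (82 in total); expected loss 20%; planned enrolment 50 per group (100 in total); power 80%; confidence level 95%, taken as a 5% significance level; mean difference 18.13.

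**1. Reproducing the plan's figure.** Adding 20% to the requirement per group gives 41 × 1.2 = 49.2, rounded up to 50, so 2 × 50 = 100. This matches the plan. On the total, 82 × 1.2 = 98.4, rounded up to 99, or 100 in equal groups.

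**2. Number remaining at the stated loss.** 100 × (1 − 0.20) = 80, and 50 × 0.80 = 40 per group. The shortfall is 82 − 80 = 2, or 1 per group.

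**3. Loss that 100 can absorb.** 1 − 41/50 = 0.18, so 18%, or 9 per group.

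**4. Enrolment that would keep 41 per group at 20% loss.** 41/0.8 = 51.25. With 51 per group, 51 × 0.8 = 40.8, which is below 41. With 52 per group, 52 × 0.8 = 41.6, which is enough. The total is 104, which is 4 more than planned.

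**5. Effect on power.** The 82 cannot be recomputed because the standard deviation is not stated. The calculation therefore assumes that 41 is the smallest number per group giving 80% power in a two-sample t-test at the 5% level. That confines the standardised difference d to a narrow band, from the value at which 41 gives exactly 80% up to the value at which 40 would already do so.

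| Test | d | Power at 40 per group |
|---|---|---|
| Two-sided | 0.626 to just under 0.634 | 79.0% to just under 80.0% |
| One-sided | 0.554 to just under 0.561 | 79.1% to just under 80.0% |

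Both cases are shown because the sample-size text does not state sidedness, while the analysis section writes the alternative directionally ("H1: G1 > G2; p < 0.05"). The choice makes almost no difference.

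**6. Effect on the detectable difference (two-sided).** If 18.13 is detectable with exactly 80% power at 41 per group, the corresponding difference at 40 per group is 18.13 × 0.6343/0.6263 = 18.36, an increase of 1.3%. This is the upper limit.

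Steps 2 to 4 use only 82, 20% and 100. They do not depend on the standard deviation, the sidedness or the 18.13.

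**The case against.** The strongest counter-argument concerns the base of the 20%. When the Sample size sentence mentions the loss, the only participants named so far are the 82, and BIAS CONTROL describes the method as adding 20%. If the 20% is a share of the 82, expected loss is 0.20 × 82 = 16.4, so 100 − 16.4 = 83.6 remain and there is no shortfall. On that reading the plan has followed its own method without error.

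This explains how 50 per group arose, but it is the less natural reading. An expected loss rate ordinarily applies to everyone enrolled, and 16.4 out of 100 is a loss of about 16%, not 20%. Even on this reading the sentence needs to state its base.

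The second argument is that the effect is negligible, and this largely stands. The worst case is one participant per group and about one percentage point of power. If 41 was rounded up from just above 40, almost no power is lost. Uncertainty in the unstated standard deviation matters more: if 41 per group gives exactly 80% power, a standard deviation 5% larger than assumed would bring power down to about 76% even with all 41 per group. The plan to collect ample contact details may also improve retention, but it does not change the arithmetic.

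It is also fair to say that a power figure reconstructed by a reviewer is a weaker basis for protocol text than one computed by the study team from its own inputs.

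**Conclusion.** The concern holds as a minor arithmetic error. With 20% of those enrolled lost, the planned 100 leaves 80 (40 per group), 2 below the stated requirement of 82. The enrolment target is sufficient only for loss of up to 18%. The conclusion rests on reading mortality as loss and on applying the 20% to those enrolled.

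The power range of about 79–80% further assumes that 41 per group is the minimum for 80% power, which the document does not allow a reader to verify. The trial is not made materially underpowered. The stated figures simply do not agree with one another.

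**What to change.** Restate the Sample size paragraph along these lines:

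> Outcome data are required from 82 participants (41 per group). We will randomise 100 (50 per group), which allows for loss of up to 18% (9 per group). At 20% loss, 80 (40 per group) would remain and power would be about 79–80%, assuming that 41 per group is the minimum for 80%.

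The study team should preferably replace the last figure with the power computed from its own standard deviation. The loss-allowance wording under BIAS CONTROL should be aligned with the new paragraph, including the base of the percentage.

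The cost is this rewording, with no extra participants. If the team prefers to keep 41 per group at 20% loss, it would need to randomise 52 per group (104 in total), which is 4 more participants.
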